10.3. Vital Signs

Vital signs (systolic blood pressure, diastolic blood pressure, pulse rate, temperature, weight, and height) will be summarized descriptively. Descriptive statistics (sample size, mean, standard deviation, median, Q1, Q3, minimum and maximum) of baseline, post-baseline, and change from baseline values for each parameter will be provided by treatment group for all scheduled time points. Summaries of vital sign data will be provided for the SAF analysis set. No inferential statistics will be generated. Vital sign values will also be listed.

10.4. Concomitant Medications

Concomitant medication verbatim terms on case report forms will be mapped to Anatomical Therapeutic Chemical (ATC) Class and Preferred Names using the World Health Organization (WHO) Drug Dictionary version 01Sep2018. Concomitant medications will be summarized (number and percentage of subjects) by ATC class and preferred name and provided by treatment group. Multiple medications (by preferred name) will be counted once only per subject. The summary will be sorted alphabetically by ATC class and then by decreasing total frequency within preferred names. Additionally, a summary of the frequency of IVIG/PLEX rescue medications will be provided. Summaries of concomitant and rescue medications will be provided for the SAF analysis population. No inferential statistics will be generated.

Concomitant medications will be defined as medications that started or were ongoing on or after the date of the first dose of study drug. Prior medications will be defined as medications that stopped prior to the first dose of study drug. All medications will be listed along with a flag to indicate whether the medication was a prior medication or a concomitant medication.

Concomitant and rescue medications will be summarized separately for the OLE. Concomitant medications in the OLE will be defined as medications that started or were ongoing on or after the date of the first dose of study drug in the OLE. Summaries of concomitant and rescue medications in the OLE will be provided for the OLE analysis population.

The following algorithms will be applied to missing and incomplete start and stop dates:

Start Dates:

If the day portion of the start date is missing, then the start date will be estimated to be equal to the date of first dose of study drug, provided the start month and year are the same as the first dose of study drug and the stop date is either after the first dose of study drug or completely missing. Otherwise, the missing day portion will be estimated as "01."

If both the day and month portions of the start date are missing, then the start date will be estimated to be equal to the date of first dose of study drug, provided the start year is the same as the first dose of study drug and the stop date is either after the first dose of study drug or completely missing. Otherwise, the event will be assumed to start on the first day of the given year (e.g., ??-??-2013 is estimated as 01-JAN-2013).

If the start date is completely missing and the stop date is either after the first dose of study drug or completely missing, the start date will be estimated to be the first day of study drug

dosing. Otherwise, the start date will be estimated to be the first day of the same year as the stop date.

Stop Dates:

If only the day of the stop date is unknown, the day will be assumed to be the last of the month (e.g., ??-JAN-2013 will be treated as 31-JAN-2013).

If both the day and month of the stop date are unknown, the stop date will be assumed to be last day of the year (e.g., ??-??-2013 will be treated as 31-DEC-2013).

If the stop date is completely missing, and the stop date will be imputed using the last known date on the study.

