### 3.2.2. Dose rationale

In MG, RVT-1401 treatment is expected to lead to a significant reduction in the levels of pIgG such as anti-AChR-IgG and anti-MuSK-IgG that are considered to be a primary driver of disease pathology. Available evidence suggests that reducing the levels of pIgG in MG is associated with clinical benefit. For example, the use of IVIG treatment has been shown to reduce AChR autoantibodies by ~30% from baseline and this is associated with clinical improvement [Liu, 2010]. Recently, data with another anti-FcRn compound (ARGX-113, efgartigimod), reported clinical improvement on the Quantitative Myasthenia Gravis (QMG) and Myasthenia Gravis-Activities of Daily Living (MG-ADL) scores with an approximate 80% reduction in total IgG and 50% reduction in AChR-IgG after once weekly administration for 4 weeks [Howard, 2018]. These data provide a target range for potentially therapeutic PD effects; however it is unknown whether there is a minimum threshold for pIgG reduction that translates into clinical efficacy.

RVT-1401 is designed to provide patients with a treatment option that allows home administration via subcutaneous (SC) injection. This significantly reduces the burden that an IV infusion treatment (e.g., IVIG, Soliris® and other anti-FcRn treatments in development) places on patients who will be required to go to an infusion center to receive their treatment.

Two dosing regimens of RVT-1401 will be assessed in double-blind phase of this study. Both will involve once weekly SC injections:

- Dosing Regimen A -680 mg weekly for 6 weeks, and
- Dosing Regimen B - 340 mg weekly for 6 weeks

Given that there is a practical limit on the volume that can be administered via SC injection, these two doses represent what can be administered as a single SC injection (340 mg) and two SC injections (680 mg) per week with the current formulation.

The OLE will involve 1 dosing regimen as a single SC injection:

- 340 mg every 2 weeks for 6 weeks

The OLE dose of 340 mg every 2 weeks will allow for the exploration of the effect of less frequent dosing of RVT-1401. This dose comprises a less frequent regimen with a convenient single SC injection. Since the frequency of dosing will decrease, the drug exposure over the dosing interval for subjects who were on active drug will decrease by approximately 8- 10 -fold for Regimen A and by 1-2 fold for Regimen B.

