## 5.3. Treatment Arms and Duration

In the double-blind phase of the study, participants will be randomized 1:1:1 to one of the three blinded treatments illustrated in Figure 2.

In the OLE an additional 3 doses over a 6-week period (every 2 weeks) will be administered, illustrated in Figure 3.

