## 6. PARTICIPANT POPULATION

### 6.1. Type and Number of Participants

A sufficient number of participants will be enrolled to achieve approximately 21 evaluable participants. Enrollment is competitive.

In order to manage the total study enrollment, the Sponsor may suspend screening and/or enrolment at any site or study-wide at any time.

If participants prematurely discontinue the study, additional replacement participants may be enrolled at the discretion of the Sponsor.

Deviations from inclusion and exclusion criteria are not allowed because they can potentially jeopardize the scientific integrity of the study, regulatory acceptability or participant safety. Therefore, adherence to the criteria as specified in the protocol is essential.

To determine participant eligibility at screening, a single repeat of certain tests such as laboratory values, vital signs, or ECGs is allowed at the discretion of the Principal Investigator.

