## **10. STATISTICAL CONSIDERATIONS AND DATA ANALYSES**

### **10.1. Sample Size Considerations**

The sample size for this study was not determined using statistical methods. The sample size was chosen based on clinical and recruitment considerations. However, the sample size of 14 active and 7 placebo participants will allow the study to show a 33% difference between either active arm and the placebo arm, assuming 90% power, equal standard deviations of 20 and an alpha of 0.05 using a two-sided z-test for the primary endpoint of percentage change from baseline in IgG at Week 7.

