To ensure robustness of analysis conclusions against parametric assumptions, rank analogues will be executed as sensitivity analysis. If the PPS differs from the FAS by more than 10%, the analyses will be replicated on the PPS. If the PPS and the FAS do not differ by more than 10%, analysis may not be done on the PPS. Final judgments will be made at the blinded data review meeting in accordance with ICH E9.

All analyses will be done using the intent-to-treat (ITT) principle.

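### The SAP foresees IVIG or plasma exchange as rescue but states no strategy for the IgG, anti-AChR and responder values recorded after it

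*SAP*

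**What the plan says.** SAP 10.4 provides that "a summary of the frequency of IVIG/PLEX rescue medications will be provided", on the safety set and without inference, and repeats this for the open-label extension. Medications are also listed.

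The visible analysis sections do not mention rescue:
- **SAP 8 (estimand)** raises infections as an intercurrent event that could disturb the efficacy scales. It assigns no strategy to them and does not name rescue.
- **SAP 9.3** runs the primary ANCOVA on the full analysis set and adds: "All analyses will be done using the intent-to-treat (ITT) principle". Its observed-cases analysis removes nothing. Responders are compared by Fisher's exact test.
- **SAP 9.4.2** takes as the responder denominator everyone with a value at the visit.
- **SAP 5.5** covers values that are missing, not values observed after rescue.

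Protocol 3.2.2 says what IVIG does to one of the measured variables and to symptoms: "the use of IVIG treatment has been shown to reduce AChR autoantibodies by ~30% from baseline and this is associated with clinical improvement".

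**The concern.** Rescue here is not an ordinary background change of medication. IVIG is itself IgG, and plasma exchange removes IgG. Percentage change in total IgG is the primary efficacy endpoint, and anti-AChR-IgG follows it in the testing sequence (H03, H04). By the protocol's own account IVIG also brings clinical improvement, so a rescued participant can reach the MG-ADL, QMG or MGC response threshold because of the rescue and be credited to the assigned arm. H06 tests MG-ADL responders.

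The stated objective is to examine what RVT-1401 does to IgG and anti-AChR-IgG. A Week 7 value taken after rescue reflects the assigned treatment plus the rescue. In arms of about seven, one such participant has a weight of one seventh.

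**Working it through.** **Inputs.** The protocol plans a "sample size of 14 active and 7 placebo participants", "randomized 1:1:1 to one of the three blinded treatments", so 21/3 = 7 per arm. Planning values: "33% difference between either active arm and the placebo arm, assuming 90% power, equal standard deviations of 20 and an alpha of 0.05", with a "two-sided z-test for the primary endpoint of percentage change from baseline in IgG at Week 7". The anti-AChR effect of IVIG (about −30%) and the expected IgG reductions (75–80% for 680 mg, 65–70% for 340 mg) come from Protocol 3.2.2. The documents give no rescue rate and no size for the effect of rescue on total IgG.

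**Step 1: the plan's own figure.**
- 7 v 7: SE = 20 × √(1/7 + 1/7) = 10.69. Power at 33 points = Φ(33/10.69 − 1.960) = Φ(1.127) = 87.0%, not 90%. The difference detectable at 90% power is (1.960 + 1.282) × 10.69 = 34.65.
- 14 v 7: SE = 20 × √(1/14 + 1/7) = 9.26. Power is 94.6% and the detectable difference 30.0.

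Neither reading gives 90% at 33 points. That is a side finding; the point here does not depend on it.

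**Step 2: anti-AChR-IgG.** With k rescued placebo participants, each shifted by −30 points, the arm mean moves by k × (−30)/7. The placebo variance becomes 400 + p(1−p) × 30², with p = k/7. SD 20 and a 33-point contrast are borrowed from the IgG statement (assumption).
- k = 1: shift −4.3, contrast 28.7, placebo SD 22.6, SE = √(400/7 + 510.2/7) = 11.40. Power = Φ(28.7/11.40 − 1.960) = 71%, against 87% with no rescue.
- k = 2: shift −8.6, contrast 24.4, placebo SD 24.2. Power 54%.

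**Step 3: total IgG.** Assume rescue shifts one participant by 60 or 120 points toward the other arm. Take a 65-point true contrast (the low end of the protocol's expectation, placebo unchanged) and SD 20 in both arms.
- 60 points: shift 60/7 = 8.6, contrast 56.4. Variance in the affected arm = 400 + (1/7)(6/7) × 60² = 840.8. SE = √(400/7 + 840.8/7) = 13.3, so z ≈ 4.2.
- 120 points: shift 17.1, contrast 47.9. Variance = 2163.3, SE = 19.1, so z ≈ 2.5.

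Both exceed 1.96.

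**Step 4: responders.** Response counts are assumed for illustration; p is two-sided Fisher.

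| Comparison | Placebo 0/7 | Placebo 1/7 | Placebo 2/7 |
|---|---|---|---|
| Combined active 10/14 | 0.004 | 0.024 | 0.159 |
| Single dose 5/7 | 0.021 | 0.103 | 0.286 |

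One rescued placebo participant counted as a responder moves the result one column to the right. In the combined test, 0/7 to 1/7 stays below 0.05; 1/7 to 2/7 does not.

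**Step 5: would the per-protocol analysis catch it?** SAP 9.3 calls for replication when the per-protocol set differs from the full set by more than 10%. Two of 21 excluded is 9.5%, so replication is not required; three of 21 is 14.3%, so it is.

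**The case against.** The strongest reply is that ITT on all analyses already implies a treatment-policy reading, which is a legitimate estimand. That stands in part: keeping post-rescue values would be defensible if the SAP chose it openly for rescue. It does not, and it plans no visible rescue sensitivity analysis. Nor does the SAP say in words that post-rescue values are kept; this follows from the analysis set, the ITT principle and the absence of any other rule.

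A second reply is that other routes exist. SAP 6.3 lets receipt of an excluded concomitant treatment be a major deviation, and blinded review could remove that participant from the per-protocol set. But that analysis is not primary and is discretionary at or below the 10% difference. It is also unclear whether on-study IVIG or plasma exchange is excluded: exclusion criterion 3 covers only a period before Screening, and Protocol 7.9.2 otherwise refers to a reference manual that is not among the documents. Concomitant medication is a covariate in the imputation model, but that model only fills in missing values. The exploratory section, SAP 9.5, is not visible, so something relevant could be there.

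A reader might infer that rescue will be commoner on placebo and so pull the tests toward no difference. That is plausible but undocumented. The one documented effect, the fall in AChR antibody after IVIG, would push H03 and H04 away from the null if it occurred in an active participant. SAP 8.1 reports that blinded review raised infections; nothing shows that rescue occurred before Week 7.

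**Conclusion.** The gap is real: an event that the SAP foresees, and that acts on the measured variables, has no stated strategy. If rescue occurs before Week 7, the plan as written mixes its effect into the PD and responder results.

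The size is conditional. One placebo case with a 30-point fall costs 4.3 points on anti-AChR-IgG. Power falls from 87% to 71% only on the borrowed IgG planning values. One extra placebo responder can move Fisher's p across 0.05, depending on the starting counts. The shift from 0.021 to 0.103 belongs to a single-dose 7 v 7 test. H06 is worded for either dose against placebo and reads most naturally as 14 v 7, where the same extra responder gives 0.004 to 0.024.

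A reader might also infer that one rescue could overturn the primary total IgG result. The documents do not support that. Against the reduction the protocol expects, the contrast stays significant even with an assumed 120-point shift in one participant. The weight of the point lies on anti-AChR-IgG and the responder endpoints.

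**What to change.** Before unblinding, add to SAP 8 and 9.3:

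1. **Responders.** A participant given IVIG, subcutaneous immunoglobulin or plasma exchange before the Week 7 assessment counts as a non-responder on MG-ADL, QMG and MGC.
2. **Total IgG, subclasses and anti-AChR-IgG.** In one analysis, exclude values after first rescue and handle them by the already planned MMRM or multiple imputation, using pre-rescue data. Report it beside the all-observed-data ITT analysis, and state which is primary.
3. **Apply rule 2 even if only one participant is affected, and to all these variables.** SAP 5.5 takes the latest available value when a single participant has missing data. For someone rescued early on active drug, that would present an early IgG value as Week 7, before the nadir that the protocol expects by the fifth dose. The imputation rule is also written for the primary endpoints, while SAP 9.1 calls the subclasses and anti-AChR-IgG supportive.

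The cost is a few lines of text and two derivations from medication dates that are already recorded. The downside is that a few observed values are lost from one of the two PD analyses, which counts with 7 per arm; the all-data analysis still uses them.

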5. GENERAL CONSIDERATIONS FOR DATA ANALYSES

Data will be listed and summarized. Listings will be sorted by treatment, participant, day, and time and include both scheduled and unscheduled visits; table summaries will be presented by treatment include placebo, RVT-1401 340 mg, RVT-1401 680 mg, combined RVT-1401 group, and by scheduled visit.

Open label extension period will start from the date of the first OLE dose for each subject. Unless otherwise specified, data collected during OLE period will be included in the same listings, tables, and figures with data collected during double-blind period.

Unless stated otherwise, descriptive summaries for continuous variables will include n, mean, standard deviation (SD), median, first and third quartiles (Q1, Q3), minimum, and maximum. The geometric mean with associated 95% confidence interval (CI) and the between-participant coefficient of variation (CV) (%CVb) for PK parameters only will also be included. For categorical variables, n and percent will be used as summary statistics. Baseline is the last available assessment prior to time of the first dose unless it is specified otherwise. If there are multiple assessments collected on the same scheduled time, the average of these assessments will be used. For tabulated safety summaries, only the scheduled assessments will be included in the summary tables.

In general, summary statistics for raw variables will be displayed as follows: minima and maxima will be displayed to the same number of decimal places as the raw data. Means, medians, and quartiles will be presented to 1 more decimal place than the raw data ; standard deviations will be presented to 2 more decimal places than the raw data.

The numbers of decimal places for summary statistics of derived variables (i.e., variables that are not measured by the study site but are calculated for analysis based on other measured variables) will be determined on a case by case basis.

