10.1.5. Treatment-Emergent Adverse Events

10.1.5.1. Definition of Treatment-Emergent

Adverse events will be classified by study part according to the following:

- Pre-treatment: AEs that either started prior to the date of the first dose of study drug or had no recorded start date and the stop date is prior to the first dose of study drug.
- Treatment-emergent: AEs that either started on or after the date of the first dose of study drug and on or before the date of 6 weeks (42 days) post the last dose of study drug or had no recorded start date and the stop date is not before the first dose of study drug.
- Post-treatment: AEs that started after the date of 6 weeks (42 days) post the last dose of study drug.
- OLE treatment-emergent: AEs that either started on or after the date of the first dose of study drug in the OLE.

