10.1.6. Summaries of Adverse Events

All AE summaries will be provided separately for the double-blind treatment period and the follow-up period as well as the OLE treatment period and OLE follow-up period. Double-blind treatment period AE summaries will present treatment-emergent AEs which occurred before study drug administration during OLE study period or before the primary lock date, whichever comes first. Follow-up period AE summaries will present post-treatment AEs, OLE treatment period AE summaries will present OLE treatment-emergent AEs which occur before or on week 12 visit and OLE follow-up period AE summaries will present OLE post-treatment AEs. Pre-treatment AEs will be listed.

Overall summaries of treatment-emergent AEs by treatment group will be provided to include the number and percentage of subjects who:

1. Had any AE,
2. Had any Grade 3 or higher AE,
3. Had any treatment-related AE,
4. Had any Grade 3 or higher treatment-related AE,
5. Had any SAE,
6. Had any treatment-related SAE,
7. Permanently discontinued from study drug due to an AE, and
8. Died.

Summaries (number and percent of subjects) of treatment-emergent adverse events (by SOC, and PT) will be provided by treatment group for the following:

- All AEs,
- All Grade 3 or higher AEs,
- All treatment-related AEs,
- All Grade 3 or higher treatment-related AEs,
- All SAEs,
- All treatment-related SAEs,
- All AEs that leading to permanently discontinued from study drug.

Multiple events will be counted once only per subject in each summary. For data presentation, SOC will be ordered alphabetically, with PT sorted by decreasing frequency in

the combined RVT-1401 column. Treatment period and follow-up period AE summaries will be provided for the SAF analysis population. Open-label extension AE summaries will be provided for the OLE analysis population. Whole study AE summaries include the double blinded period, OLE period and follow up will be provided for below 3 tables:

- Overall summaries of treatment-Emergent AEs
- Treatment-emergent AEs by SOC and PT
- Serious treatment-emergent AEs by SOC and PT

In addition to the by-treatment AE summaries, data listings will be provided for the following:

- Pre-treatment AEs
- Treatment-emergent AEs
- Post-treatment AEs
- OLE treatment-emergent AEs
- SAEs
- Liver events
- AEs leading to discontinuation or interruption of study drug
- Deaths
- Grades 2-4 albumin events

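### SAP 10.4 gives the main concomitant-medication and IVIG/PLEX rescue summaries a start but no end, so, read literally, they mix double-blind use with OLE and follow-up use

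*SAP*

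**What the plan says.** SAP Section 10.4 defines the main window: "Concomitant medications will be defined as medications that started or were ongoing on or after the date of the first dose of study drug". The layout is by arm: "Concomitant medications will be summarized (number and percentage of subjects) by ATC class and preferred name and provided by treatment group". Rescue gets one sentence: "Additionally, a summary of the frequency of IVIG/PLEX rescue medications will be provided". That sentence names neither a period nor columns; the columns follow from the general rule in SAP Section 5, under which "table summaries will be presented by treatment include placebo, RVT-1401 340 mg, RVT-1401 680 mg, combined RVT-1401 group, and by scheduled visit". The population is the safety set, which SAP Sections 5.1 and 5.3 group by actual double-blind treatment.

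SAP 10.4 also plans a separate concomitant and rescue summary for the OLE population. It starts at the first OLE dose and likewise has no end. Nothing says that medications in that summary leave the main one. SAP Section 5 sets the default the other way: OLE data share the same outputs as double-blind data unless the SAP specifies otherwise.

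Adverse events are treated differently. Under SAP 10.1.6 the double-blind tables hold "treatment-emergent AEs which occurred before study drug administration during OLE study period or before the primary lock date, whichever comes first", and follow-up, OLE and OLE follow-up events have their own summaries. Three pooled tables are added and labelled as such: "Whole study AE summaries include the double blinded period, OLE period and follow up will be provided for below 3 tables". Exposure (SAP 6.2.1) and adherence (SAP 6.2.2) are also split between the double-blind and OLE periods.

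**The concern.** A by-arm rescue table is naturally read as rescue on RVT-1401 against rescue on placebo. With an open window it can hold three other things: rescue in a former placebo participant now on open-label 340 mg, shown under placebo; rescue in a former active participant after weekly dosing has stopped, shown under RVT-1401; and rescue in an OLE decliner during the treatment-free follow-up. The table has no visit dimension, so the reader cannot see which is which. Laboratory and vital-sign tables run by scheduled visit and do not have this problem.

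The double-blind count matters for interpretation. Protocol Section 3.2.2 reports that IVIG lowers AChR autoantibodies by about 30%, and anti-AChR-IgG at Week 7 is in the SAP 9.2 testing sequence. A reader will want to know how many participants in each arm had IVIG or plasma exchange before that readout, and the planned summary does not isolate them.

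There is also a timing problem. The primary analysis is triggered when the last participant completes Week 7 (Protocol 10.2.2, SAP Section 3). Earlier participants may by then have OLE or follow-up data, so an open window would differ in length between participants at that lock. The double-blind AE rule names the first OLE dose and the lock date as limits; SAP 10.4 names neither.

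**Working it through.** The plan states no figure on this point, so there is none to reproduce. The check applies the written date rules to nominal study days.

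**Inputs**
- Week k = Day 7(k − 1) + 1, which matches the Time and Events Tables (Week 2 = Day 8, Week 6 = Day 36).
- First OLE dose at Week 8 (Protocol 5.1): 7 × 7 + 1 = Day 50.
- Last visit at Week 18: 7 × 17 + 1 = Day 120.
- Last double-blind dose at Week 6: Day 36.
- Treatment-emergence limit for AEs (SAP 10.1.5.1): "on or before the date of 6 weeks (42 days) post the last dose of study drug".

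**OLE participant.** Each rule is applied to illustrative start days, assuming the primary lock falls later than these days:

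| Start day | Main medication/rescue table | OLE medication/rescue table | Double-blind AE table (an AE starting that day) |
|---|---|---|---|
| 20 | yes | no | yes |
| 45 | yes | no | yes |
| 55 | yes | yes | no |
| 85 | yes | yes | no |
| 110 | yes | yes | no |

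Share of the main window after the first OLE dose: (120 − 50) / (120 − 1) = 70/119 = 58.8%. Counting both end days gives 71/120 = 59.2%. Either way it is 59%.

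**OLE decliner.** AE treatment-emergence ends at Day 36 + 42 = Day 78. The medication window runs on to Day 120, which is 120 − 78 = 42 days longer. SAP 10.4 plans no follow-up medication table. The 12-week follow-up set is optional in SAP 5.1 and recorded in SAP Section 14 as not carried over, although the protocol's section on OLE and follow-up analyses calls for separate summaries of that population.

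**Can the double-blind count be recovered from the two tables?** Not by subtraction. Each medication is counted once per participant, and one still ongoing at the first OLE dose meets both definitions. Main minus OLE is therefore not double-blind use.

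**Weight of one participant.** With 21 participants randomised 1:1:1 there are 7 per arm, so one participant is 1/7 = 14 percentage points of a column. That holds for any single event in any period and does not measure the error.

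**The case against.** The best counter-argument is that SAP 10.4 does specify otherwise: it says medications and rescue are summarised separately for the OLE, which can be read as one main table and one exclusive OLE table. That reading is fair, and it is why double counting is described here as the literal reading and not as an explicit instruction. But the sentence adds a table without removing records from the other, and it does nothing for OLE decliners, whose follow-up medication enters the main table on either reading.

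Other objections stand and limit the point:
- The summaries are descriptive, with no inferential statistics, and rescue is not a primary or secondary endpoint.
- All medications are listed, and listings are sorted by treatment, participant, day and time. With about 21 participants, rescue can be placed before or after the first OLE dose by hand.
- The major-deviation summary (SAP 6.3) may also capture excluded concomitant treatment, so a reader who took the SAP 10.4 table to be the only sight of rescue would be wrong.
- Background drugs have to be stable at entry and will mostly be ongoing from Day 1; an end date changes little for them. The issue is mainly rescue and newly started drugs.
- The AE comparator is not a simple stop at the first OLE dose: the primary lock can come first, decliners' treatment-emergence runs to about Day 78, and three AE tables pool the whole study.

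A reader might also infer that OLE rescue is charged to the randomised arm. The safety-set columns are actual double-blind treatment; the two coincide unless someone was misdosed.

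**Conclusion.** The point holds as a gap in the SAP's period definition. The main concomitant and rescue summaries have a start and no end, the SAP's pooling default draws OLE data in, and no summary confined to the double-blind period is specified. Followed as written, the by-treatment rescue table can attribute to placebo a rescue given on open-label RVT-1401, and to RVT-1401 a rescue given after weekly dosing ended.

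The size is 59% of nominal calendar days for a participant who enters the OLE, assuming visits on schedule and follow-up to Week 18. It would be tempting to read this as 59% of rescues being misplaced. That needs a constant rescue rate and universal OLE entry; the documents give no rescue rate, and the OLE is optional. The count could be zero, and the direction of any distortion is unknown. Nor do the documents support a claim that an efficacy conclusion is at risk: no estimate, test or alpha uses this table. The change is worth making because the table would be read as a comparison it does not make, and the correction is cheap.

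**What to change.** In SAP 10.4:

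1. Limit the main by-treatment concomitant and rescue summaries to medications started or ongoing from the first dose until before the first OLE dose, or until the primary lock date if earlier, as SAP 10.1.6 does for AEs.
2. Give OLE decliners a stated fixed cut-off, for example the Week 8 visit. This is deliberately shorter than the Day 78 limit for their treatment-emergent AEs, so that medication windows are comparable across participants; the SAP should say so.
3. State that medications taken only after the cut-off appear in the OLE summary or, for decliners, in a short follow-up summary. A medication ongoing across the cut-off may appear in both, and the SAP should say that too.
4. Keep the OLE columns by double-blind treatment, as SAP 5.1 requires. Everyone in the OLE receives the same regimen, so columns by current treatment would hide the placebo switchers.
5. Label any table that pools all periods as a whole-study table, as the AE section does.

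The cost is a few sentences, a date filter in the programming and one additional small follow-up table. No data collection changes.
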